7.3.1.2.2. Time to Progression

TTP is defined as the interval of time between the date of first dose and the earlier of the date of first documented evidence of PD, or death due to PD, whichever occurs first.

A summary of the assignments for progression and censoring dates for TTP are specified in [Table 6](#)

Table 6 Assignments for Progression and Censoring Dates for TTP Analysis

Situation	Date of Event (Progression/Death) or Censoring	Outcome Event (progression/Death) Or Censored
No (or inadequate) baseline tumor assessments ^[1] and the subject has not died (if the subject has died follow the rules for death indicted at the bottom of the table)	First dose date	Censored
No post-baseline assessments and the subject has not died (if the subject has died follow the rules for death indicted at the bottom of the table)	First dose date	Censored
Progression documented at or between scheduled visits	Date of assessment of progression ^[1]	Event
No progression (or death)	Date of last 'adequate' assessment of response ^[2]	Censored
New anticancer treatment started (prior to documented disease progression or death) ^[3] .	Date of last 'adequate' assessment of response ^[2] (on or prior to starting anti-cancer therapy)	Censored
Death from causes other than progression	Date of death	Censored
Death or progression after an extended loss-to-follow-up time (two or more missed cycles + 7 day window) ^[4]	Date of last 'adequate' assessment of response ^[2] (prior to missed assessments)	Censored

[1] In part 1, adequate baseline assessment is defined as at baseline, a patient has at least one of the following measurements: a. Serum M-protein or b. Urine M-protein or c. Serum FLC assay or d. Biopsy proven plasmacytoma (should be measured within 28 days of Screening Visit).

In part 2, adequate baseline assessment is defined as at baseline, a patient has at least one of the following measurements: a. Serum M-protein ≥ 0.5 g/dL (≥ 5 g/L) or b. Urine M-protein ≥ 200 mg/24h or c. Serum FLC assay: Involved FLC level ≥ 5 mg/dL (≥ 50 mg/L) and an abnormal serum free light chain ratio (<0.26 or >1.65) or d. Biopsy proven plasmacytoma (should be measured within 28 days of Screening Visit and no later than the first dose date).

[2] An adequate assessment is defined as an assessment where the Investigator determined response is sCR, CR, VGPR, PR, MR, or SD.

[3] If PD and New anti-cancer therapy occur on the same day assume the progression was documented first e.g., outcome is progression and the date is the date of the assessment of progression). If anti-cancer therapy is started prior to any adequate assessments, censoring date should be the date of first dose. Refer to Section 16.5.4 "Extended Loss to Follow-up or Extended Time without an Adequate Assessment".

TTP will be summarized using Kaplan-Meier curves. If there are a sufficient number of progressions or death due to PD, median TTP, first and third quartiles and 95% CI, will be estimated using the Brookmeyer-Crowley method [Brookmeyer, 1982]. A figure and listing of TTP time will also be provided. Summary and figure of TTP will be based on Part 2 MM population; listing of TTP will be based on All Treated MM population.

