7.3.1.2.3. Duration of Response

Duration of Response (DOR) is defined, for subjects with a confirmed response (PR or better) as the time between first documented evidence of confirmed response and disease progression or death due to PD, whichever occurs first.

- Duration of response is derived for patients with a confirmed PR or better only.
- Censoring rules will follow those of the TTP analysis.

DOR will be summarized using Kaplan-Meier curves. If there are a sufficient number of progressions or death due to PD among the responders, median DOR, first and third quartiles and 95% CI, will be estimated using the Brookmeyer-Crowley method [Brookmeyer, 1982]. A figure and listing of DOR time will also be provided. Summary and figure of DOR will be based on Part 2 MM population and subgroup: prior anti-cancer therapy of interest; listing of DOR will be based on All Treated MM population.

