16.2.3. Dose Expansion

16.2.3.1. Every 3 Weeks Dosing Schedule for Multiple Myeloma

Time and Events Table for Full Study (Cycle = 21 days)									
Study Assessments ¹	Screen ²	Day 1 C1	Day 8 C1	Day 15 C1	Day 1 C2	D1 of C3-C16	End of Study Treatment ³⁴	Monthly Follow up ³⁵	
Baseline Demographics	X								
Medical History	X								
Physical Exam	X	X			X	At the start of each cycle	X		
Ocular Exam	X ³				X ⁴	At the start of each cycle ⁴	X ⁴	X ³⁵	
ECOG Performance Status	X				X	At the start of each cycle	X		
Vital Signs (BP, HR, Body Temperature)	X	X ⁵	X	X	X ⁵	At the start of each cycle ⁵	X		
Weight and Height	X	Weight only			Weight only	Weight only - At the start of each cycle	Weight only		
Hematology	X	X ⁶	X	X	X	At the start of each cycle	X		
Clinical chemistry	X	X ⁶	X	X	X	At the start of each cycle	X		
Urine Dipstick	X	X ⁶			X	At the start of each cycle	X		
INR, PTT	X	X ⁶	X	X	X	At the start of each cycle			
HBV/HCV tests	X								
CK-MB , Troponin	X ^{7,8}		X ^{7,8}		X ^{7,8}	At the start of each cycle ^{7, 8}	X ^{7,8}		
BNP	X ⁹								
UPEP and urine Immunofixation	X				X	At the start of each cycle			
SPEP and serum immunofixation and Serum M-protein Calculation	X				X	At the start of each cycle			
Kappa, lambda free LC, FLC ratio	X				X	At the start of each cycle			

CONFIDENTIAL

BMA117159

Time and Events Table for Full Study (Cycle = 21 days)									
Study Assessments ¹	Screen ²	Day 1 C1	Day 8 C1	Day 15 C1	Day 1 C2	D1 of C3-C16	End of Study Treatment ³⁴	Monthly Follow up ³⁵	
24 hr urine protein and albumin	X				X	At the start of each cycle			
IgG, IgM, IgA	X				X	At the start of each cycle			
CRP, beta2 microglobulin	X				X	At the start of each cycle			
Pregnancy Test	X ¹⁰					At the start of cycles 5 ¹⁰ , 9 ¹⁰ , 13 ¹⁰	X ¹⁰	X ¹¹	
Chest X-ray	X								
12-lead ECG	X ¹²	X ¹²	X ¹²	X ¹²	X ¹²	At the start of each cycle ¹²	X ¹²		
LVEF and valves assessment (ECHO)	X ¹³					At the start of cycles 4 ¹³ , 9 ¹³	X ¹³		
Extramedullary Plasmacytoma Imaging	X ¹⁴					At the start of cycles 5 ¹⁴ , 9 ¹⁴ , 13 ¹⁴	X ¹⁴		
BM Aspirate (see below for each test required within procedure):									
Disease assessment	X ¹⁵					At the time of Complete Response			
BCMA assessment and PD (flow)	X ¹⁶		X ^{16, 18}						
FISH testing	X ¹⁷								
BM biopsy for disease assessment	X ¹⁹					At the time of CR (disease assessment only)			
Serum (soluble BCMA)		X ²⁰			X ²⁰	Predose at the start of each cycle	X		

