16.5.4. Extended Loss to Follow-up or Extended Time without an Adequate Assessment

For subjects, if two or more scheduled disease assessments are missed and are then followed by an assessment of PD or death, PFS will be censored at the last adequate assessment prior to PD or death. When the scheduled disease assessment is every 3 weeks, a window of 49 days (6 weeks + 7 day window) will be used to determine whether there was an extended time without adequate assessment. That is, if the time difference between PD/death and last adequate assessment is more than 49 days, then PFS will be censored at the last adequate assessment prior to PD/death.

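### SAP Table 6 gives two censoring dates for a non-PD death more than 49 days after the last adequate assessment, with no order of precedence for TTP or DOR

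*SAP*

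**What the plan says.** SAP Section 7.3.1.2.2 defines TTP as the time from first dose to "the earlier of the date of first documented evidence of PD, or death due to PD, whichever occurs first". A death from another cause is therefore never an event and has to be censored. Three rows of Table 6 matter here:

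- "No progression (or death": censored at the last adequate assessment.
- "Death from causes other than progression": censored at the date of death. The row sets no limit on the time since the last assessment.
- "Death or progression after an extended loss-to-follow-up time (two or more missed cycles + 7 day window": censored at the last adequate assessment. The row is not restricted to deaths due to PD.

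A separate row censors subjects who start new anticancer treatment before PD or death at the last adequate assessment on or before that start.

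The notes to Table 6 refer to Section 16.5.4. There, for three-weekly assessments, "a window of 49 days (6 weeks + 7 day window) will be used", and when the gap is longer, "then PFS will be censored at the last adequate assessment prior to PD/death". For DOR, Section 7.3.1.2.3 says "Censoring rules will follow those of the TTP analysis".

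**The concern.** A non-PD death after a long gap meets two rows that give different dates. For PFS, the text of Section 7.3.1.2.1 settles the matter: the extended-gap rule holds whatever is learned later about progression or death. The TTP and DOR text has no such sentence.

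The choice affects the estimates. Under the date-of-death row, a subject whose progression can no longer be observed stays in the risk set as progression-free until death. An otherwise identical subject who is still alive stops at the last adequate assessment, and so does the same subject's PFS. This pushes Kaplan-Meier TTP and DOR upward. If the plan is silent, the programmer must choose with the data in hand, in an open-label study where DOR is also reported in three small subgroups.

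**Working it through.** **1. The window.** Two three-week assessments plus 7 days: 2 × 21 + 7 = 49 days, as Section 16.5.4 states. That is 49 / 30.4375 = 1.61 months.

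**2. Both rows applied to example subjects** (illustrative days from first dose, no PD, no new therapy, death from another cause; months = days / 30.4375):

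| Last adequate assessment | Death | Gap | Date-of-death row | Extended-gap row | Difference |
|---|---|---|---|---|---|
| day 63 | day 100 | 37 days | 3.29 months | does not apply | none |
| day 63 | day 180 | 117 days | 5.91 months | 2.07 months | 3.84 months |
| day 84 | day 365 | 281 days | 11.99 months | 2.76 months | 9.23 months |

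Once the gap exceeds 49 days, the two rows differ by the whole gap. For the third subject, PFS is censored at day 84 under Table 5. TTP would be censored at day 84 or day 365, depending on the row.

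**3. Can such gaps occur?** In the Part 2 myeloma schedule (Section 16.2.3.1), "SPEP and serum immunofixation and Serum M-protein Calculation" is marked at screening and at cycle starts, with no entry at end of treatment or monthly follow-up. The urine electrophoresis and free light chain rows follow the same pattern. Footnote 29 has survival followed for a year from the last subject's last dose. Deaths can therefore be recorded long after routine M-protein assessment has stopped.

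**4. Size if the date-of-death row wins.** The documents give no rates, so every rate below is an assumption. The first simulation used 40 subjects, exponential TTP with a median of 8 months, 3-5% per month leaving treatment without PD, then 3-6% per month dying of other causes, a 24-month cut-off, and no new therapy. Between 8% and 19% of subjects met both rows. Affected subjects were censored at the last assessment or at death:

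| Scenario | 12-month TTP: last assessment / death | Median, months: last assessment / death |
|---|---|---|
| low | 0.352 / 0.385 | 8.0 / 8.5 |
| middle | 0.353 / 0.409 | 7.9 / 8.9 |
| high | 0.354 / 0.430 | 8.0 / 9.4 |

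The median shifts by 0.5, 1.0 and 1.4 months, and 12-month TTP by 3.3, 5.6 and 7.6 percentage points.

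A second simulation assumed a true median of 7.9 or 12.0 months, a median of 12 to 48 months to stopping without PD, and a median of 180 days from stopping to non-PD death. Between 11% and 39% of subjects met both rows, and 12-month TTP rose by 2 to 11 percentage points. Those inputs deliberately include high non-PD death rates.

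**5. Size if the extended-gap row wins.** With the rates of the first simulation, the median is 7.99-8.03 months, against 7.98-8.01 when every non-PD death is censored at the last assessment. Twelve-month TTP is 0.353-0.356 against 0.353-0.354.

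**6. Effect of the new-therapy row.** The first simulation's rates were kept, the date-of-death row was applied, and an assumed rate of starting new therapy after leaving treatment was added:

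| New therapy per month | Subjects in both rows | Median TTP (months) |
|---|---|---|
| 10% | 3.6-8.9% | 8.2-8.6 |
| 20% | 1.9-5.0% | 8.1-8.3 |
| 40% | 0.8-2.1% | 8.0-8.1 |

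At 20-40% per month, that is roughly 0 to 2 of 40 subjects (0.008 × 40 = 0.3; 0.050 × 40 = 2.0).

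**The case against.** The strongest reply is that the extended-gap row is the specific exception and the non-PD death row the general case. Table 5 has the same layout, the PFS text says that the exception prevails, and Table 6 repeats the row and points to Section 16.5.4. On that reading TTP and DOR already follow the rule and, by step 5, there is almost no bias. This is the more natural reading, and a reader who infers that the plan as written inflates TTP and DOR goes too far: that follows only if the other row is applied. It remains an inference, however. The overriding sentence stands only in the PFS section, and Section 16.5.4 directs only how PFS is censored.

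Three further points stand. The new-therapy row removes many of the subjects concerned. Survival follow-up of subjects who finished before protocol amendment 5 depends on re-consent. Disease assessment does not end entirely with the cycles: plasmacytoma imaging is scheduled at end of treatment, and Section 16.5.5 uses responses from unscheduled visits. All three limit the number and length of the gaps; none removes the conflict.

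It is also tempting to move every non-PD death to the last adequate assessment. The documents do not require that. The plan tolerates gaps of up to 49 days, and re-dating deaths inside that window would be a preference rather than a correction.

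**Conclusion.** The contradiction can be read directly from Table 6 and needs no assumption: a non-PD death more than 49 days after the last adequate assessment, with no new anticancer therapy, has two censoring dates, and nothing ranks them for TTP or DOR. The direction of bias is conditional: upward if the date of death is used, negligible if the extended-gap row is used.

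Its size in this trial is unknown. The 8-19% of subjects and the shift of 0.5-1.4 months in the median rest on assumed rates, ignore the new-therapy row, and are upper-end figures, not a forecast. TTP and DOR are exploratory endpoints in a single-arm cohort with no hypothesis test, so the impact is limited. A one-line clarification is still worthwhile, because the rule fixes reported dates and should not be chosen after the data are seen.

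**What to change.** State in Table 6 that the extended-loss-to-follow-up row takes precedence over the non-PD death row. Equivalently, limit the date-of-death row to deaths within 49 days of the last adequate assessment. In Section 16.5.4, name TTP and DOR alongside PFS. DOR then follows through its existing reference to the TTP rules.

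The cost is one line in the table and a few words in Section 16.5.4. TTP and DOR estimates may be slightly shorter than under date-of-death censoring. No data collection changes.

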7.3.1.2.3. Duration of Response

Duration of Response (DOR) is defined, for subjects with a confirmed response (PR or better) as the time between first documented evidence of confirmed response and disease progression or death due to PD, whichever occurs first.

- Duration of response is derived for patients with a confirmed PR or better only.
- Censoring rules will follow those of the TTP analysis.

DOR will be summarized using Kaplan-Meier curves. If there are a sufficient number of progressions or death due to PD among the responders, median DOR, first and third quartiles and 95% CI, will be estimated using the Brookmeyer-Crowley method [Brookmeyer, 1982]. A figure and listing of DOR time will also be provided. Summary and figure of DOR will be based on Part 2 MM population and subgroup: prior anti-cancer therapy of interest; listing of DOR will be based on All Treated MM population.

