7.2.1. Multiple Myeloma

7.2.1.1. Endpoint / Variables

7.2.1.1.1. Overall Response Rate

Overall Response Rate (ORR), is defined as the percentage of responders (subjects with confirmed stringent complete response (sCR), complete response (CR), very good partial response (VGPR), and partial response (PR) as assessed according to 2011 International Myeloma Working Group (IMWG) criteria (Appendix 1 in the protocol)). Only the assessments from the start of treatment up to the earlier of disease progression or the start of new anti-cancer therapy will be considered. Only new systemic anti-cancer drugs taken are considered as anti-cancer therapy (radiotherapy and surgeries are not considered as systemic anti-cancer therapy for the purpose of this analysis). .

Subjects with only one assessment (therefore not confirmed), or assessments of Not Evaluable or missing response will be treated as non-responders; i.e. they will be included in the denominator when calculating the percentage.

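### Duration of response takes over a TTP censoring row that ends at first dose, so a living confirmed responder with an inadequate baseline would get a negative duration

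*SAP*

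**What the plan says.** Section 7.3.1.2.3 defines DOR as "the time between first documented evidence of confirmed response and disease progression or death due to PD, whichever occurs first". It adds two rules: "Duration of response is derived for patients with a confirmed PR or better only", and "Censoring rules will follow those of the TTP analysis". No exception or adaptation follows.

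The TTP rules are in Table 6 of Section 7.3.1.2.2. TTP has a different origin: it is counted from first dose, not from response. The first row of Table 6 covers "No (or inadequate) baseline tumor assessments" in subjects who have not died and censors them at the first dose date. Deaths are sent elsewhere: "if the subject has died follow the rules for death indicted at the bottom of the table".

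Footnote 1 of Table 6 defines adequacy. For Part 1, any one of the listed measurements suffices. For Part 2 it begins "In part 2, adequate baseline assessment is defined as at baseline, a patient has at least one of the following measurements" and attaches numerical thresholds to serum M-protein, urine M-protein and serum FLC, with a biopsy-proven plasmacytoma inside a time window as the alternative.

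On the response side, Section 7.2.1.1.1 begins "Overall Response Rate (ORR), is defined as the percentage of responders" and refers to the 2011 IMWG criteria in the protocol. Neither that section nor the confirmation algorithm in 7.2.1.1.2 mentions baseline adequacy.

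**The concern.** A censoring table written for an interval that begins at first dose has been applied unchanged to one that begins at response. For TTP, the first row gives a time of about zero, which is coherent. For DOR, the same calendar date lies before the interval has begun.

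If such a responder exists, the plan instructs the programmer to produce an impossible value. The subject then drops out of the DOR summary and curve (Table 2.0081, Figure 12.0051) or appears with a negative duration in Listing 1.0570. The DOR denominator would no longer match the responders behind the ORR. The same value passes into the DOR variables of the exposure-response dataset (Section 16.10.1). Because the row spares subjects who died, retention in the analysis would also depend on outcome.

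A second question is what happens when such a responder progresses. Two rows of Table 6 then apply and give different answers: censored at first dose, or an event at the progression date.

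**Working it through.** The SAP gives no figure to reproduce. The check is date arithmetic plus a reading of each Table 6 row.

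**Inputs**
- DOR start: date of first confirmed response. Under 7.2.1.1.2 this is the date of the first of the two consecutive assessments. Under 16.5.5, disease assessments are post-baseline.
- End date under the first row of Table 6: first dose, Day 1.
- Cycle length: 21 days, so nominal Cycle *k* Day 1 is Day 1 + 21(*k* - 1). The visit window is ±3 days.
- Design figures: ORR of 40% under the alternative and up to 40 Part 2 MM subjects (Sections 2.3 and 2.4).

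**Negative duration**

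DOR = end date - response date. The value with one day added is in brackets, since Section 7.3.1.2.3 does not state the convention.

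| First response at | Study day | DOR if censored at first dose |
|---|---|---|
| C2D1, 3 days early | 19 | 1 - 19 = -18 (-17) |
| C2D1 | 22 | 1 - 22 = -21 (-20) |
| C3D1 | 43 | 1 - 43 = -42 (-41) |
| C4D1 | 64 | 1 - 64 = -63 (-62) |
| C6D1 | 106 | 1 - 106 = -105 (-104) |

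The result is negative at every scheduled response visit checked, and more so the later the response.

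**Other rows of Table 6**
- No post-baseline assessment: cannot describe a responder.
- New therapy before any adequate assessment (footnote 3, first dose date): cannot describe a countable response, because 7.2.1.1.2 stops counting at the start of new therapy.
- All remaining rows give a date on or after the response. With response on Day 22 and one day added: last adequate assessment at C3D1 (Day 43) gives 22 days; at C6D1 (Day 106), 85 days; PD at C7D1 (Day 127), 106 days; non-PD death on Day 141, 120 days.

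Only the inadequate-baseline row causes the problem.

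**Progression in an affected responder**

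The first row gives censoring at first dose. The progression row gives an event at the progression date. Table 6 sets no order between them. The PFS text in 7.3.1.2.1 censors at first dose for lack of an adequate baseline without making an exception for later progression. That suggests the first row overrides, but it is PFS text, not TTP or DOR text.

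**Size**

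Expected responders at the design rate: 0.40 × 40 = 16. One affected responder is 1/16 = 6.25% of the DOR sample; two are 2/16 = 12.5%. The SAP gives no count, so the range of 0 to 2 is an assumption.

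**The case against.** The strongest counter-argument is that the case may not occur. Response is assessed under IMWG criteria held in a protocol appendix, which was not available for this check. A measurable-disease condition for assigning PR could be there. All Treated is worded as eligible subjects, and eligibility may require measurable disease. Section 7.3.1.3 notes that with a normal baseline FLC ratio no percent reduction in the FLC difference is available, so for that marker a response would be hard to document. In Part 1 the case is close to empty: any one measurement is enough, and the schedule takes all three laboratory measures at screening.

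Much of this stands. It limits how often the case arises and confines it mainly to Part 2. It does not remove it. The SAP wrote an inadequate-baseline row because it expects such subjects, and it tabulates eligibility deviations within All Treated, so they are not necessarily excluded. A plasmacytoma measured outside the Part 2 window, with no other criterion met, makes the baseline inadequate, yet the SAP text does not bar an investigator-assessed PR. Nothing in the SAP floors DOR at zero or exempts these responders. The exposure-response specification sets DOR to zero only for non-responders.

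The objection on importance also stands. DOR is exploratory and descriptive, the DOR summaries omit hazard ratios and p-values, and a negative value would be conspicuous in the listing.

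A reader might infer that observed progressions are certainly discarded. The documents do not establish that, because Table 6 sets no precedence. A reader might also infer that every responder with an inadequate baseline is affected. Those who died follow the death rules and are not.

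**Conclusion.** The rule is wrong as written, within narrow limits. A living confirmed responder with no or an inadequate baseline is assigned a negative DOR, about -21 days for a response at nominal Cycle 2 Day 1, and cannot enter the Kaplan-Meier estimate. If that responder later progresses, the plan does not say whether the progression counts. It is lost only if the first row is read as overriding, as the PFS text suggests.

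The effect is 6.25% of the DOR sample per affected responder at 16 responders, or 0 to 12.5% under the assumed 0 to 2. The true number is not in the document, is probably small and may be zero. The conclusion assumes that the response criteria in the protocol do not themselves require an adequate baseline as Table 6 defines it. ORR does not change, nor does any primary or secondary endpoint or the futility rule. Severity is minor.

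**What to change.** Keep the sentence "Censoring rules will follow those of the TTP analysis" and extend it with a reference to Table 6 and this exception: *except that the inadequate-baseline row does not apply to DOR; all other rows apply unchanged.* Add a footnote to the DOR summary giving the number of responders whose baseline was inadequate under footnote 1 of Table 6.

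The exception should go no further than that. A rewrite that censored all non-progressing responders at their last adequate assessment would conflict with the row that censors non-PD deaths at the date of death. One that counted every progression as an event would conflict with the rows on new therapy and extended loss to follow-up. With the first row removed for DOR, a documented progression falls under the progression row, subject to those retained rows, and the precedence question disappears.

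The cost is one clause in the SAP, one condition in the derivation and one footnote. TTP, PFS and ORR are untouched.
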